### 6.7.3. Analysis of Secondary Efficacy Endpoints

All analyses of secondary efficacy endpoints will use the mITT population. Sustained remission rate will be based on the adjudication outcome. Local assessments of ESR, CRP, and imaging will be used for other secondary efficacy endpoints.

#### 6.7.3.1. Sustained remission rate at Week 26

Subjects who complete the treatment period without a flare by week 26 will be considered to have sustained remission. The sustained remission rate at week 26 can be obtained from the estimates of time to flare at week 26 by using the Kaplan-Meier method, along with their standard errors using Greenwood's formula. Comparison with p-value will be conducted between the treatment groups. Two-sided p-value and 95% CI calculated using normal approximation.

#### 6.7.3.2. Time to elevated ESR by week 26

Time to elevated ESR will be defined as the time from randomization to earliest date of an ESR value of  $\geq 30$  mm/hr. All subjects who do not have an elevated ESR by week 26/ EOT will be censored at last assessment date or the randomization date, whichever is later.

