- If a study site or clinic visit coincides with the subject’s scheduled dose, study treatment will be administered at the study site or clinic. Study drug treatment should be dispensed as necessary to the subject for home administration to ensure dosing compliance. Investigator staff may contact patients between visits to ensure compliance with protocol-specified treatment regimens.
- New-onset subjects can have an optional temporal artery biopsy taken at Screening (or otherwise available from diagnostic workup) and Week 26 as part of the study. For relapsing/refractory patients, if the subject has not had a prior a temporal biopsy an optional biopsy can be done at Screening and Week 26. If the subject has an existing biopsy sample available this can be submitted as the screening/predose sample and an optional biopsy can be performed at Week 26.
- Chest X-ray (or high res CT), DLCO, and PFTs should be obtained at Screening, or existing documentation (if available) within 12 weeks of Day 0 can be used and reviewed by the Investigator or designee.
- PFTs and DLCO should be performed at Screening within 16 weeks prior to Day 0 (or documented report available from PFT &/or DLCO from within 12 weeks prior to Day 0). They should also be performed at Weeks 12 and 26 and 38 with a window of ±14 days.
- Subjects will be given prednisone as necessary and instructed to dose in alignment with their prednisone taper. Investigator staff may contact patients between visits to ensure compliance with protocol specified treatment regimens.
- Clinical decisions for determination of inclusion and flare will be based upon local laboratory values either ESR and/or CRP.
- The imaging technique used during screening to diagnose GCA should be repeated at week 26 for the study. If ultrasound is available at screening for diagnosis of GCA this should be conducted again at weeks 12, 26 and 38, or in case of a suspected flare of GCA with no other imaging (MRI, CT/CTA or PET-CT) required. If MRI, CT/CTA or PET-CT was used at screening for diagnosis of GCA and no ultrasound is available, the same imaging technique used at screening should be repeated at week 26 or as necessary for diagnosis in case a suspected flare.
- Ultrasound imaging if clinically relevant should be performed at or before Day 0 to support clinical remission decision making unless there is no evidence of temporal artery inflammation and diagnosis of GCA is confined to large vessels (By MRI or CT).

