12.2.4 CRP and ESR

Central laboratory assessments of CRP and local assessment of ESR will be performed at each study visit. Centrally determined laboratory values will be used for statistical evaluations and report writing. CRP changes and the time course to decrease and resolve CRP to normal values ≤ 0.5 mg/dL will be assessed.

If necessary local CRP tests can be used by the site to support the Investigator's clinical decisions regarding the GCA status.

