12.6 Laboratory Assessments

Laboratory assessments should be collected as per the schedule of activities ([Table 1](#)). Unscheduled laboratory assessments for safety issues are permitted as deemed necessary by the Investigator. The procedures for the collection, handling, and shipment of laboratory samples are specified in the Laboratory Manual supplied to sites by the central laboratory.

Local laboratory tests and values may be used by the Investigator as necessary to support clinical decisions but will not be captured as part of the study for analysis.

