### **6.3. Demographics and Baseline Disease Characteristics and History**

Demographic and other baseline characteristics will be summarized by descriptive statistics for each treatment group and overall for the SAF. They will also be presented in by-subject listings.

Descriptive statistics will be provided for the following:

- age
- weight (kg)
- height (cm)
- body mass index (BMI) (kg/m^2)

Frequency tabulations will be presented as collected in the eCRF for:

- age (< 65 years or ≥ 65 years)
- sex
- race
- ethnicity
- substance use (tobacco) history (cigarettes, cigars, pipes, or chewing tobacco).

Disease history such as disease status (new-onset or relapsing/refractory), prior GCA (yes/no), biopsy (yes/no), imaging (yes/no), and prior treatment will be summarized using frequencies and percentages and presented in by-subject listings. Time since diagnosis to randomization (month), ESR value for eligibility and at baseline, and CRP value for eligibility and at baseline (local and central separately) will be summarized by descriptive statistics.

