#### **6.8.2. Clinical Laboratory Parameters**

Laboratory assessments should be collected as per the schedule of assessments, starting at Screening, Baseline, Week 4, Week 12, Week 20, Week 26/EOT, and Final Safety Follow-up/Week 38.

Unscheduled laboratory assessments for safety issues are permitted as deemed necessary by the Investigator. Local laboratory tests and values may be used by the Investigator as necessary to support clinical decisions.

Clinical laboratory assessments are listed in [Table 3](#).

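### The SAP takes CRP for two ordered secondary endpoints from the local laboratory, but the protocol schedules post-baseline CRP only at the central laboratory and assigns central values to the statistics

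*SAP*

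**What the plan says.** SAP 6.7.3, on the secondary endpoints other than sustained remission: "Local assessments of ESR, CRP, and imaging will be used for other secondary efficacy endpoints". Two of these endpoints use CRP. They are time to elevated CRP (6.7.3.3) and completed taper with normal CRP (6.7.3.7), third and seventh in the order of SAP 3.2. Neither subsection names another source.

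Protocol 12.2.4 assigns the laboratory test by test: "Central laboratory assessments of CRP and local assessment of ESR will be performed at each study visit". It continues: "Centrally determined laboratory values will be used for statistical evaluations and report writing". Local CRP has a limited role there: "If necessary local CRP tests can be used by the site to support" clinical decisions about GCA status. Protocol 12.6 says that local laboratory values "will not be captured as part of the study for analysis". SAP 6.8.2 repeats the first part of that sentence ("Local laboratory tests and values may be used by the Investigator as necessary to support clinical decisions") without the clause on capture.

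Protocol Table 1 marks central CRP and local ESR at every visit. It marks local CRP only at Screening, Day 0 and unscheduled visits. A footnote adds: "Clinical decisions for determination of inclusion and flare will be based upon local laboratory values either ESR and/or CRP".

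SAP 7.1 lists departures from the protocol, including small ones such as the numbering of Day 1. It has no item on the source of CRP.

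**The concern.** A programmer who follows SAP 6.7.3 would select the local CRP records. If sites follow Table 1, local CRP after baseline arises mainly at unscheduled visits, which worsening symptoms or safety issues prompt. Whether a subject has a value then depends on how that subject is doing.

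The SAP's own rules turn a missing value into a result. Time to elevated CRP takes its censoring from the ESR table (SAP Table 2), where row 4 censors a subject with no post-baseline assessment at randomization. Under 6.7.3.7, a subject with no CRP after taper completion cannot be a responder. Both rules fall on subjects who stay well.

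Both endpoints are in the fixed testing sequence of SAP 6.7.1. If testing reaches time to elevated CRP and that test fails, six endpoints below it lose formal testing, among them cumulative steroid dose at Week 26.

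**Working it through.** **Visit count (protocol Table 1).** Scheduled post-baseline visits through Week 26 are Weeks 1, 2, 3, 4, 8, 12, 16, 20, 24 and 26, which makes 10. Marked at these visits: central CRP 10, local ESR 10, local CRP 0.

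**Visits after taper completion (protocol Table 3 with the completion rule in SAP 6.7.3.6).** Starters at 20 to 35 mg reach 0 mg in Week 23 or 24, so the Week 24 and Week 26 visits can count. Starters at 40 to 60 mg complete around Weeks 25 to 26, so Week 26 counts and at most also Week 24. That gives 1 or 2 scheduled central values and 0 scheduled local values.

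**What the loss could be.** The plan gives no power figure for these endpoints and no local testing rate. What follows is an illustration that borrows the planning rates for flare.

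Those rates reproduce the plan's own figure for the primary endpoint:
- HR = ln 0.85 / ln 0.50 = 0.234.
- Expected events = 42 × 0.15 + 28 × 0.50 = 20.3.
- Schoenfeld power with 20 events at 3:2 is about 0.89, against the stated 87%.

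*Time to elevated CRP.* The set-up is 42 vs 28 subjects, two equal strata, exponential times with 85% vs 50% free of elevation at Week 26, and a stratified log-rank test at two-sided 0.05 with KPL-301 better. There were 2,000 simulated trials, with a Monte Carlo standard error of about 0.01. With central CRP, where elevation is found at the next scheduled visit, power is 0.896. With local CRP:

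| Local testing pattern | 10% | 20% | 30% | 50% |
|---|---|---|---|---|
| A. At most one unscheduled test, every elevation caught when it occurs | 0.14 | 0.29 | 0.39 | 0.60 |
| A. Same, half of elevations caught | 0.13 | 0.23 | 0.32 | 0.46 |
| B. Test at each scheduled visit with this probability, elevations found only there | 0.43 | 0.68 | 0.79 | 0.87 |
| B. Same, half also caught when they occur | 0.60 | 0.77 | 0.84 | 0.90 |
| B. Same, all also caught when they occur | 0.71 | 0.84 | 0.88 | 0.90 |

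Subjects of 70 with no post-baseline local value:
- A, all caught: expected event-free subjects are 42 × 0.85 + 28 × 0.50 = 49.7. Multiplying by (1 − rate) gives about 45 / 40 / 35 / 25.
- B, found only at visits: 70 × (1 − p)^10 gives about 24 / 8 / 2 / 0.

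Pattern A loses power even when every elevation is recorded, because the event-free subjects leave the risk set at time zero. KPL-301 is expected to have more of them (35.7 against 14).

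*Completed taper with normal CRP.* Assumed true success is 85% vs 50%, with the same chance of a local test per post-taper visit in both arms. The counted rate is the true rate × p with one visit, or × [1 − (1 − p)²] with two. Power comes from exact binomial enumeration of a Mantel-Haenszel-type z test with one stratum. With central CRP it is 0.889.

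| | 10% | 20% | 30% | 50% |
|---|---|---|---|---|
| One visit: counted rates | 8.5 vs 5% | 17 vs 10% | 25.5 vs 15% | 42.5 vs 25% |
| One visit: power | 0.04 | 0.11 | 0.19 | 0.33 |
| Two visits: counted rates | 16.1 vs 9.5% | 30.6 vs 18% | 43.3 vs 25.5% | 63.7 vs 37.5% |
| Two visits: power | 0.10 | 0.23 | 0.33 | 0.57 |

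**The case against.** The best counter-argument is that local may mean reported by the site and not adjudicated. The preceding sentence of SAP 6.7.3 speaks of the adjudication outcome, and the same phrase covers imaging, for which neither document describes a central read. That reading is possible. However, SAP 6.3 uses the word for the laboratory, "CRP value for eligibility and at baseline (local and central separately", and nothing in 6.7.3.3 or 6.7.3.7 points to central values. If central was meant, the same sentence needs the same correction.

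The clause in protocol 12.6 cannot be literally global. Local ESR is scheduled and analysed, and SAP 6.3 summarizes local CRP at eligibility and baseline. This stands, and the case rests on protocol 12.2.4 and Table 1.

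A count of 0 of 10 scheduled marks is not a count of data. Flare decisions use local values, so some post-baseline local CRP will exist, and sites may run it more often than Table 1 asks. This also stands. But the Table 1 footnote accepts either marker, so a site relying on local ESR needs no local CRP even at a suspected flare.

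The power figures rest on assumed rates. Flare requires a marker and a sign or symptom, so flare rates are not CRP rates. The figures also ignore the baseline-CRP exclusion and censoring at early end of treatment. They show direction and range and do not estimate the loss.

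**Conclusion.** The concern holds. SAP 6.7.3 contradicts protocol 12.2.4 and Table 1 on the source of CRP for two ordered secondary endpoints, and SAP 7.1 does not declare the change. What the documents establish is 0 of 10 scheduled local values against 10 of 10 central values, and missing-value rules that count against well subjects.

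The effect on power is conditional. It is severe for both endpoints if local CRP is confined to occasional unscheduled tests. It is negligible for time to elevated CRP if local tests are frequent, and it disappears for both if sites run local CRP at every visit. Time to elevated CRP matters only if the primary, sustained remission and ESR tests all succeed first, and none of those three is affected. The correction should be made, but the primary conclusion does not depend on it.

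**What to change.** In SAP 6.7.3, name central CRP as the source for 6.7.3.3, including its baseline-CRP exclusion, and for 6.7.3.7. Keep local ESR, which agrees with the protocol. Use local CRP in a supportive analysis only.

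If the sponsor does intend local CRP, SAP 7.1 should declare and justify it and say how subjects with no post-baseline local value are handled. A declaration would not supply the missing values.

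The cost is about one sentence before database lock. No new data are needed, because central CRP is already planned at each visit.

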### **1.3. Sample Size Justification**

The sample size calculation was based on the assumption that time to flare follows an exponential distribution and the proportion of subjects without a flare by week 26 will be 50% in placebo and 85% in KPL-301, the median time to flare would be approximately 26 weeks in placebo arm and 111 weeks in KPL-301 arm. The hazard ratio (KPL-301 vs. placebo) would be approximately 0.234. With a 2-sided significance level of 0.05 and a 3:2 randomization ratio for KPL-301 vs. placebo, it would require approximately 20 events to achieve 87% power using a two-sided log rank test.

Approximately 70 subjects will be randomized by disease stratum (new-onset or relapsing/refractory) to receive KPL-301 or placebo at a 3:2 allocation ratio.

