#### **6.7.1. Multiplicity Adjustment**

Multiplicity adjustment with respect to the primary efficacy and secondary efficacy endpoints will be adjusted using the gate-keeping hierarchical testing procedure. The hierarchy order of the secondary endpoints is presented in Section 3.2. For each endpoint, the null hypothesis is that there is no treatment difference between KPL-301 and placebo. The alternative hypothesis is that KPL-301 is superior to placebo. For each test, the 2-sided type I error rate is 0.05. The primary endpoint will be tested first. If the 2-sided p-value is  $\leq 0.05$ , statistical significance of the primary endpoint will be claimed, and the next hierarchical endpoint will be tested. This process will continue until an endpoint is not statistically significant.

There is no adjustment for other endpoints.

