**Table 1: Censoring Rules for Time to Flare by Week 26**

	Scenario	Event or Censoring	Censoring Reason	Date of Event or Censoring
1	Flare occurrence on or prior to week 26	Event	No censoring	Date of flare
2	No flare occurrence on or prior to week 26	Censored	No flare occurrence	Date of last assessment by week 26
3	No flare occurrence on or prior to EOT	Censored	No flare occurrence by EOT	Date of last assessment by EOT
4	No post baseline assessment	Censored	No assessment	Date of randomization

Time to flare by week 26 will be summarized by the 25th, 50th (median), and 75th percentiles calculated using the Kaplan-Meier (KM) method to estimate the survival functions for each treatment group. The 95% confidence interval (CI) for the percentiles will be calculated using a log-log transformation. Plots of survival curves by treatment using the KM method will be presented. Additional survival plots will be provided by treatment for the stratification factor.

A log-rank test stratified by the stratification factor (disease status) will be used as the primary treatment comparison between KPL-301 and placebo. To describe the magnitude of treatment effect, the hazard ratio for KPL-301 compared to placebo and the corresponding Wald 95% CI will be

calculated based on a Cox proportional-hazards model with treatment as a covariate and stratified by the stratification factor.

If subjects were randomized based on incorrect stratum, then the corrected stratum will be used for stratified analyses rather than the incorrect stratum recorded at randomization.

The primary analysis of time to flare will be based on the adjudication outcome. Time to flare per investigator's assessment will be used as a supportive analysis of the primary endpoint. A 2x2 table of concordance will be used to assess the agreement between adjudicated and investigator assessments.

As a sensitivity analysis, the stratified analyses of time to flare based on adjudication will be repeated for the per protocol analysis set defined in Section 2.3 .

The stratified analyses of time to flare based on adjudication will also be repeated for the mITT analysis set by censoring subjects without flare before EOT at the last assessment date by week 26. That is, the censoring does not take into consideration of the early treatment discontinuation. The scenario 3 in the censoring table follows scenario 2 rule.

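### Sustained remission at Week 26, the first gated secondary, is compared without the disease-status stratum that every other gated test uses; the power cost is small (minor)

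*SAP*

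**What the plan says.** SAP 6.7.3.1 reads the sustained remission rate off the time-to-flare Kaplan-Meier curves at Week 26, with Greenwood standard errors. On the comparison it says only: "Comparison with p-value will be conducted between the treatment groups. Two-sided p-value and 95% CI calculated using normal approximation". Protocol 14.5.2 adds no more than that the rate is estimated and compared by the Kaplan-Meier method. Neither document uses the word unstratified. That is read from silence, but it is how a programmer would implement the paragraph.

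Every other gated test names the stratum. For the primary, SAP 6.7.2 states: "A log-rank test stratified by the stratification factor (disease status) will be used as the primary treatment comparison between KPL-301 and placebo". SAP 6.7.3.2 to 6.7.3.4 use the same stratified log-rank test and Cox model, 6.7.3.5 puts the factor in the ANCOVA, and 6.7.3.6 to 6.7.3.8 use stratified Cochran-Mantel-Haenszel tests.

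SAP 3.2 lists sustained remission first among the secondaries. On the sequence, SAP 6.7.1 says "For each test, the 2-sided type I error rate is 0.05" and "This process will continue until an endpoint is not statistically significant".

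**The concern.** When the strata differ in flare risk, a test that ignores them uses a standard error larger than the design warrants, so it is less sensitive than the stratified primary on the same adjudicated flares. Because the endpoint is the first gate, a miss here after a positive primary would bar formal claims on the eight remaining entries in SAP 3.2, including cumulative steroid dose, which is a stated secondary objective.

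Protocol 8.1 gives a reason to expect a difference: it describes initial disease as responsive to glucocorticoids and chronic disease as resistant, and all subjects are on a steroid taper.

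**Working it through.** **Inputs.** SAP 1.3 assumes that "the proportion of subjects without a flare by week 26 will be 50% in placebo and 85% in KPL-301", and derives a hazard ratio of 0.234 from it. On power, the same section states that "it would require approximately 20 events to achieve 87% power using a two-sided log rank test". The planned size there is about 70 subjects, allocated 3:2 within disease stratum. Protocol 8.6: 42 KPL-301 and 28 placebo. Protocol synopsis: half the subjects in each stratum, so 21 and 14 per stratum. Assumed, because the current text gives no figures: dropout of 0%, 10% or 20% by Week 26, and the stratum-specific rates shown below.

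**The plan's own figure.** HR = ln 0.85 / ln 0.50 = 0.2345. Expected events = 28 × 0.50 + 42 × 0.15 = 20.3. Schoenfeld power at 20 events = Φ(√(20 × 0.6 × 0.4) × |ln 0.2345| − 1.96) = Φ(1.218) = 88.8%, within 2 points of the stated 87%.

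**Pooled or unpooled variance, no dropout.** Unpooled SE = √(0.25/28 + 0.1275/42) = 0.1094; z = 0.35/0.1094 = 3.20; power = Φ(3.20 − 1.96) = 89.2%. Pooled: overall rate (14 + 35.7)/70 = 0.71; null SE = √(0.71 × 0.29 × (1/28 + 1/42)) = 0.1107; power = Φ((0.35 − 1.96 × 0.1107)/0.1094) = 88.8%. Leaving the variance unpooled does not cost power.

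**Why the stratum matters, no dropout.** Stratified randomisation fixes the mix in each arm, so the true sampling error is the within-stratum one, while the planned test divides by 0.1094.
- Strata 60/90 and 40/80 (placebo/KPL-301): within-stratum SE = √(0.24/28 + 0.125/42) = 0.1075. Planned power = Φ((0.35 − 1.96 × 0.1094)/0.1075) = 89.7%; stratified = Φ(0.35/0.1075 − 1.96) = 90.3%.
- Strata 70/95 and 30/75: within-stratum SE = √(0.21/28 + 0.1175/42) = 0.1015. Planned = 90.9%; stratified = 93.2%.

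**Simulation at the planned effect, 10% dropout** (20,000 trials per row; Monte Carlo error about 0.2 points; stratified column uses equal stratum weights and Greenwood variance):

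| Placebo/KPL-301 by stratum | Stratified log-rank | Week 26 as planned | Week 26 stratified | Primary significant, gate fails: planned | Same, stratified |
|---|---|---|---|---|---|
| 50/85, 50/85 | 89.3% | 87.7% | 88.4% | 2.2% | 1.7% |
| 60/90, 40/80 | 90.3% | 88.3% | 89.5% | 2.6% | 1.7% |
| 70/95, 30/75 | 92.2% | 88.8% | 91.7% | 3.8% | 1.5% |

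A repeat run with equal strata, a 20-point and a 40-point placebo gap gave 88.1% vs 88.7%, 88.2% vs 89.7% and 88.1% vs 91.1%, with the gate failure falling from 1.8–4.3% to 1.4–2.0%. Without dropout the three gains in the table's scenarios are 0.2, 0.7 and 2.3 points. With 20% dropout they are 0.6 (equal strata) and 3.3 (40-point gap).

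**Weaker effect, 10% dropout.** Strata 70/90 and 30/70 (average 50% vs 80%): 73.8% planned vs 77.9% stratified, gate failure 6.9% vs 3.8%. Strata 70/88 and 30/62 (average 50% vs 75%): 56.3% vs 63.5%, gate failure 9.5% vs 4.3%.

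**Two-sided type I error, 10% dropout.**
- Planned test, equal strata: 5.8% (50% flare-free) and 6.3% (71%); about 5.6 to 6.8% across runs.
- Planned test, unequal strata (85% and 57%): 5.1%; other runs with unequal strata gave 4.1% and 4.7%.
- Stratified with plain Greenwood variance: about 6 to 7%.
- Stratified with the null variance: about 5.1 to 5.4%; one smaller run of 4,000 trials gave 5.7% with equal strata.
- Planned-test rejections in favour of KPL-301 only: 2.8%, 2.7% and 2.1% in the three null scenarios, against a nominal 2.5%.

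**Arms with no flares.** At 95% flare-free, the chance that all 21 subjects in a stratum arm are flare-free is 0.95^21 = 34% without dropout. Greenwood variance is then zero. In simulated trials of the 70/95, 30/75 scenario with 10% dropout, about 37% had at least one such arm.

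**The case against.** A Kaplan-Meier difference with Greenwood errors is a standard, valid comparison and agrees with Protocol 14.5.2. Using it unstratified for one secondary in a Phase 2 proof-of-concept trial can be called an efficiency preference. That stands, and it is why the point is minor.

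Three stronger readings are tempting, and the documents support none of them.
- A reader might infer that the unpooled normal approximation loses power. It does not (89.2% unpooled vs 88.8% pooled). Its effect is a slight excess of type I error when strata are equal. Much of that excess lies in the direction favouring placebo, and the test is reached only after a significant primary.
- A reader might infer that the chain is likely to close after a positive primary. At the planned effect this happens about 2 to 4% of the time. Part of it arises from comparing one time point instead of the whole curve, so stratifying reduces it without removing it. Steroid dose also sits behind three further gates, so this one alone does not decide that claim.
- A reader might take a loss of 4 to 7 power points as the size of the problem. Those figures need both a weaker effect than SAP 1.3 assumes and a 40-point placebo gap.

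No current text gives stratum rates. Superseded sample-size text in the Protocol's Amendment v2.0 change log had placebo remission of 30% and 10%, a 20-point gap. That makes the middle row of the table a fair guide: a gain of about 1 point.

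**Conclusion.** The omission is real and isolated: one gated test out of the whole hierarchy does not name the factor used in randomisation. Its consequence is small. At 50% vs 85% and 10% dropout, ignoring the stratum costs about 0.5 to 1 point of power with equal strata, 1 to 1.5 with a 20-point placebo gap and 3 with a 40-point gap. The chance of a positive primary with a failed gate falls from about 2–4% to 1.5–2% if the test is stratified; the loss is larger if the true effect is weaker. Type I error of the planned test is slightly above nominal with equal strata and near or below it with unequal strata. Stratifying alone would not correct the first, since plain Greenwood variance within strata leaves it at about 6 to 7%; the null variance is needed as well. All sizes rest on assumed dropout and stratum rates and on the planned 50:50 stratum mix. Severity: minor.

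**What to change.** Before unblinding, amend SAP 6.7.3.1 as follows.
1. Estimate the Week 26 Kaplan-Meier difference d_k within each disease stratum k, using the corrected stratum as elsewhere in the SAP.
2. Combine with Mantel-Haenszel weights w_k = n1k × n0k / n_k. With 21 and 14 per stratum each weight is 8.4, so the two strata count equally.
3. For the p-value use the null variance: in each stratum, the Greenwood variance of the curve for both arms pooled, times n_k × (1/n1k + 1/n0k), combined with the squared weights.
4. Report the stratum-weighted difference with a 95% CI and state the variance used for that CI.
5. Give a rule for the CI when a stratum arm has no flares and its Greenwood variance is zero. The fallback in SAP section 5 covers only strata where neither arm has an event or all responses are the same, so it does not reach this case.

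Cost: one paragraph of SAP text and a few lines of code, with no added data or patient burden. One small downside is that the p-value and the CI, built on different variances, can occasionally disagree near 0.05; the SAP should say that the p-value governs the gate.
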